## Protocol Template Form

Item 1 UTHSCSA Tracking Number	HSC20150859H
--------------------------------	--------------

Item 2 Abstract / Project Summary	Provide a succinct and accurate description of the proposed research. State the purpose/aims. Describe concisely the research design and methods for achieving the stated goals. This section should be understandable to all members of the IRB, scientific and non-scientific. DO NOT EXCEED THE SPACE PROVIDED.
-----------------------------------	--

**Purpose/Objectives:** Nausea is a common symptom encountered in the Emergency Medical Services (EMS) environment that is often treated with oral or intravenous anti-emetic medications. **Research Design/Plan:** This will be a randomized equivalence study comparing the reduction in a patient's reported level of nausea after treatment with either Ondansetron or Isopropyl Alcohol

**Methods:** Patients who report nausea and/or vomiting in the normal evaluation and care of after calling 911 for Emergency Medical Care will be offered enrollment in the study. A short script will be attached to the outside of each study packet providing information about the study and its risks and benefits. Verbal or written (waiver of informed consent will be requested) permission will be obtained to start randomization. If the patient agrees to enroll then the study packet will be opened and utilized. All Advanced Life Support Ambulances in the San Antonio Fire Department will have sealed numbered opaque boxes or envelopes with either: 70% Isopropyl Alcohol swabs or ondansetron. Six Visual Nausea Severity Scoring cards will be provided with a marking pen to record timed nausea levels before and upon arrival to the Emergency Department and 15 minutes after treatment whichever comes first.

**Clinical Relevance:** This treatment has not been studied in the unique environment encountered by Paramedics in the Pre-Hospital setting. If this treatment is found to be effective, it may offer a very simple, extremely inexpensive and non-invasive (basic life support) approach for the treatment of nausea.

Item 3 Background	

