
Step-by-Step Methods:
 
RECRUITMENT AND RANDOMIZATION PROCESS Patients who report nausea and/or vomiting in the normal evaluation and care of after calling 911 for Emergency Medical Care will be offered enrollment in the study. A short script will be attached to the outside of each study packet providing information about the study. Verbal (waiver of documentation informed consent will be requested) permission will be obtained to start randomization. If the patient agrees to enroll then the study packet will be opened and utilized.
 
PROCEDURES AND LOGISTICS All Advanced Life Support Ambulances in the San Antonio Fire Department will have sealed numbered opaque boxes or envelopes with either:
 
 
• Three large 2 ply 70% Isopropyl Alcohol swabs
 
 
OR
 
 
• Ondansetron (Zofran) 4mg for IV/IM use (standard of care)
 
 
These study packets will have similar weight, shape and contour despite the contents. If needed, props may be included to make packages similar in weight, contour or sound when shaken so as to not reveal its true contents. The goal is to enroll at least 400 patients over a 1 year period.
 
For each arm, the package will contain a step by step instruction checklist. Six Visual Nausea Severity Scoring cards will be provided with a marking pen to record timed nausea levels before and upon arrival to the Emergency Department and 15 minutes after treatment whichever comes first. The treatment protocol for each arm will be:
 
70% Isopropyl Alcohol
 
 
1. Mark Time and Visual Nausea Severity Score 0-10
 
2. Remove alcohol prep with gloved hand
 
3. Place under nares of the patient
 
	
--	--

4. Instruct the patient to take three separate deep inhalations of the Isopropyl vapors through their nose
5. Record time of treatment on back of first Visual Nausea Severity Score card.
6. Mark time and Subsequent Visual Nausea Severity Scores upon arrival to the Emergency Department at indicated time intervals.
7. If patient still has significant nausea and or vomiting after ten minutes provide rescue Ondansetron therapy with 4mg of Ondansetron slow IV push or IM
8. Mark time and Visual Nausea Severity Score upon arrival to the Emergency Department on third card.
9. Document all interventions on electronic Patient Care record as per usual procedures.

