10. Complete Paramedic evaluation tool.
11. Envelope or box, with Consent, score cards and Paramedic evaluation tool will be returned to Medic Officer on duty and a new study packet will be replaced.
12. Used Study Packets will be collected by the Investigators

Ondansetron 4mg IV/IM (standard of care)

1. Mark Time and Visual Nausea Severity Score 0-10 on first enclosed card.
2. Start IV if not already done so.
3. If unable to obtain IV access in two attempts use intramuscular route.
4. Inject 4mg of Ondansetron slow IV push or IM.
5. Record time of treatment on back of first Visual Nausea Severity Score card.
6. Mark time and Second Visual Nausea Severity Score upon arrival to the Emergency Department or 10 minutes after treatment whichever comes first.
7. If patient still has significant nausea and or vomiting after ten minutes provide rescue an additional dose of Ondansetron therapy with 4mg of Ondansetron slow IV push or IM
8. Mark time and Visual Nausea Severity Score upon arrival to the Emergency Department on third card.
9. Document all interventions on electronic Patient Care record as per usual procedures.
10. Complete Paramedic evaluation tool.
11. Envelope or box, with Consent, score cards and Paramedic evaluation tool will be returned to Medic Officer on duty and a new study packet will be replaced.
12. Used Study Packets will be collected by the Investigators.

Data Analysis Plan: A secure excel spreadsheet tool will be used to abstract data from the research data collection documents and the EMS electronic patient care record. The patient will only be identified by the randomization number, incident number, age (if greater than 89 age will be indicated by <89 years), sex and date of service in the database and on all study packet materials. All relevant time intervals and Visual Nausea Severity Scores will be recorded for enrolled patients. Time to treatment will be compared between the two arms of the study as well as changes in Visual Nausea Severity Scores. Treatment failures requiring additional Ondansetron will be characterized. Paramedic will be asked to evaluate the treatment provided for ease of use, time needed to complete the treatment and their impression of effectiveness of the assigned treatment. T-test and confidence intervals will be utilized to determine statistical significance.

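### Nausea reduction is the named comparison, but the Data Analysis Plan fixes no primary contrast, deciding time or hierarchy, so the headline result can be chosen after the data are seen

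*Combined protocol and SAP*

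**What the plan says.** The abstract (Item 2) states the aim: "This will be a randomized equivalence study comparing the reduction" in patient-reported nausea between ondansetron and isopropyl alcohol. It does not label this outcome primary and gives no equivalence margin.

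The Data Analysis Plan (end of Item 6) does not turn that aim into one deciding analysis:

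- Two kinds of outcome are compared between arms: "Time to treatment will be compared between the two arms of the study as well as changes in Visual Nausea Severity Scores".
- Treatment failures needing additional ondansetron are to be characterized; no test is stated.
- Paramedics are asked to rate "ease of use, time needed to complete the treatment and their impression of effectiveness of the assigned treatment". The text does not say that these ratings are compared between arms.
- One general sentence closes the plan: "T-test and confidence intervals will be utilized to determine statistical significance". No alpha, sidedness, hierarchy or multiplicity rule is given.

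Several post-treatment scores could supply the change in nausea. Item 6 states "Six Visual Nausea Severity Scoring cards will be provided with a marking pen", and its introduction, like the abstract, gives ED arrival or 15 minutes, whichever is first. Step 6 of the ondansetron checklist reads "Mark time and Second Visual Nausea Severity Score upon arrival to the Emergency Department or 10 minutes after treatment whichever comes first". Step 6 of the alcohol checklist refers to later scores at intervals that it does not define. Step 8 of both checklists adds "Mark time and Visual Nausea Severity Score upon arrival to the Emergency Department on third card". Step 7 of both provides for additional ondansetron if significant nausea or vomiting persists after ten minutes.

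**The concern.** The outcomes that can be compared are not interchangeable, and nothing says which one decides the trial.

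- **Early score against ED-arrival score.** The ED-arrival card can be completed after additional ondansetron. In the alcohol arm it may then reflect alcohol followed by ondansetron; in the other arm, one or two doses of ondansetron. A score taken before any additional drug reflects the assigned treatment alone. The two contrasts can lead to different conclusions, and the plan has no rule to settle that.
- **Time to treatment.** One arm inhales from a swab. The other needs an injection, with up to two IV attempts before the IM route. A difference favouring alcohol is plausible whatever alcohol does to nausea. This outcome is also the first one listed.

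At stake is whether the published conclusion answers the stated question. As the plan stands, it could rest on the score time that turned out favourably, or on speed of delivery.

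**Working it through.** **The plan's own figure.** The only design number is an enrolment goal of at least 400. It cannot be reproduced, because no effect size, SD, margin, alpha or power is given. There is no stated error rate to check.

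**Inputs from the documents.** Time to treatment is one comparison. The checklists support one or two score changes (second card, ED-arrival card). Cards four to six have no stated use and are not counted. The explicit family is therefore k = 2 or 3. Adding the three paramedic ratings would make k = 6.

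**Assumptions.** Two-sided 0.05 per test, all null hypotheses true, and correlation between test statistics from 0 to 0.8. The documents give none of these.

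**Formulas.** If independent, the family-wise rate is 1 − 0.95^k:

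- k = 2: 1 − 0.9025 = 0.0975
- k = 3: 1 − 0.8574 = 0.1426
- k = 6: 1 − 0.7351 = 0.2649

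With a common correlation ρ, the rate is 1 − P(all |Z| < 1.96) under an equicorrelated normal distribution, integrated numerically.

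| Tests | ρ = 0 | ρ = 0.5 | ρ = 0.8 |
|---|---|---|---|
| 2 (time, one score change) | 0.098 | 0.091 | 0.078 |
| 3 (time, two score changes) | 0.143 | 0.125 | 0.098 |
| 6 (plus three ratings) | 0.265 | 0.207 | 0.139 |

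With one prespecified primary contrast the rate is 0.05.

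**If time to treatment truly differs.** It is then no longer a false-positive opportunity. Two score contrasts remain, and the k = 2 row applies: 7.8% to 9.8%. On short transports in the ondansetron arm the second card is itself taken at ED arrival, which pushes the correlation up and the rate down.

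**How easily time to treatment could reach significance (illustration only).** Take 200 per arm (400 split 1:1, assumed) and a true 3-minute difference. With an assumed SD of 5 minutes, the standard error is 5 × √(2/200) = 0.5, so z = 3/0.5 = 6 and power is Φ(6 − 1.96) > 0.999. With an SD of 8, the standard error is 0.8, z = 3.75 and power is Φ(1.79) = 0.96. None of these inputs comes from the documents.

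**How often two score contrasts could disagree (illustration only).** If both have 80% power for the same true effect, exactly one is significant in 23% of trials at correlation 0.5 and in 14% at 0.8.

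**The case against.** The strongest reply is that the abstract already names one comparison, "comparing the reduction in a patient's reported level of nausea after treatment with either Ondansetron or Isopropyl Alcohol", so a time-to-treatment result would visibly fail to answer the trial's question. This has force: the aim is not undefined. But it does not choose between an early and an ED-arrival score, and the Data Analysis Plan does not tie the conclusion to either.

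A second reply is that family-wise error of difference tests is a poor measure for an equivalence study, where a significant t-test is not the success criterion. That stands. The rates above describe the plan's closing sentence, not the risk of a false claim of equivalence.

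A reader might go further and infer that six outcomes are all tested, with a false-positive rate near 21%. The documents do not support this. The paramedic ratings are only collected and the failures only characterized; testing them is an inference from the general closing sentence. The 21% also needs a common correlation of about 0.5 among all six tests, which nothing in the documents supplies. Nor can time to treatment be treated both as an almost certain true difference and as a source of false positives.

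**Conclusion.** The point holds in a limited form. No primary contrast, deciding score time or hierarchy is named, and the candidate contrasts differ in meaning, so the deciding result can be selected after the data are seen. This does not depend on any calculation.

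Its size, assuming two-sided 0.05 per test, is a family-wise rate of about 10% to 14% for the two or three explicitly planned comparisons if they are independent, and less if they are correlated. The figure of 26.5% is an upper limit that applies only if three paramedic ratings are tested too. The power and disagreement figures are illustrations. The gap should be closed, but the abstract's stated aim keeps it short of leaving the trial without a question.

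**What to change.** First, reconcile the post-treatment score times in the abstract, the Item 6 introduction, step 6 of the alcohol checklist and step 6 of the ondansetron checklist, so that the second card is taken at the same defined time in both arms. Without this, a second-card contrast could compare scores taken at different times. Which time to use is for the sponsor to decide. The 15-minute wording falls after the ten-minute point for additional ondansetron, so the reconciled text must make clear how the card relates to it.

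Then state in the Data Analysis Plan:

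- The single primary contrast is the between-arm difference in change in Visual Nausea Severity Score from the first card to that second card, recorded before any additional ondansetron.
- The trial's conclusion rests on the confidence interval for this contrast, judged against an equivalence margin that the sponsor states in advance.
- Time to treatment, the ED-arrival score change, additional ondansetron use and any comparison of paramedic ratings are secondary or exploratory. They are reported as estimates with confidence intervals, and none can stand as the trial's result.

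The analysis change is wording only and needs no extra patients or measurements. The cost lies in aligning the checklists and choosing a margin. The small downside is that the other outcomes can no longer support a stand-alone claim of significance.

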	
Behavioral strategies such as watching the true horizon, steering the vehicle, tilting head into turns and laying down with eyes closed have been shown to alleviate some symptoms of motion sickness. But these strategies are not available in the EMS environment. Scopolamine administered well before motion stimulus has been shown to prevent motion sickness and acute treatment is best when using sedating antihistamines. Non-sedating antihistamines, Ondansetron and ginger root have not been found to effectively prevent nor treat motion sickness.
 
Multiple agents have been studied for the treatment of nausea in the emergency department with equivalency of effect and time on onset. Common agents include ondansetron, metoclopramide, promethazine and prochlorperazine. Such agents have also been used in the EMS environment to some degree, but require parenteral administration with exposure to the risks for side effects or sedation. There are also no options at the BLS level. Post-operative oxygen therapy has not been shown to decrease post nausea after c-section delivery which is disappointing as this is a ubiquitous therapy in the EMS environment of care, is inexpensive and easy to administer. Ondansetron has been shown to be safe and effective in the prehospital environment with a low incidence of side effects but cost and need for parenteral administration is often a barrier to care.
 
Multiple studies have shown Isopropyl Alcohol (IPA) 70% aromatherapy to be as effective as Ondansetron with a more rapid onset of nausea relief. This therapy was performed by holding a folded saturated 70% IPA pad under the nares with the patient inhaling the vapors. The patient is simply instructed to take three deep breaths through their nose. In animal experiments, toxicity from inhalation of IPA is very low at doses allowable by inhalation as compared with dermal or oral ingestion. Dermal application of IPA is routinely used by EMS personnel to cleanse the area of skin immediately surrounding the insertion point of an intravascular catheter for medication administration, or blood draw.

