**Item 7 Risks Section:**

Complete the following table to describe the risks of all **research procedures** listed in Step 2, Institutional Form (items 28-34). *Do not list risks of Routine care procedures here.*

N/A, Risks are described in the informed consent document – do not complete this table.

Research procedures	Risks
example: 
 
• History and physical
 
• Questionnaire
 
• Laboratory tests
 
	List the reasonably expected risks under the following categories as appropriate:
Add or delete rows as needed	
Isopropyl Alcohol	Serious and likely; 
 
 none
 
 Serious and less likely; 
 
 none
 
 Serious and rare; 
 
 none
 
 Not serious and likely; 
 
 dizziness, nausea, abdominal pain
 
 Not serious and less likely 
 
 hypotension
 

Ondansetron(standard of care)	Serious and likely; 
 
 none
 
 Serious and less likely; 
 
 none
 
 Serious and rare; 
 
 decrease in urine output, uncontrolled twisting movements of the neck, trunk, arms, or legs (Dystonia), death,
 
 Not serious and likely; 
 
 confusion, dizziness, blurred vision, fixed position of the eye, hiccups, redness of the skin, fast heartbeat, fever, headache, shortness of breath, weakness,
 
 Not serious and less likely 
 
 none
 

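### No side-effect item or safety analysis is specified in Item 6, although Item 7 lists likely events in both arms, so harms cannot be reliably compared by arm as written

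*Combined protocol and SAP*

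**What the plan says.** Item 6 has three places where a side effect could be captured or analysed.

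- **Checklists.** Both arms have 12 steps. They cover scoring, treatment, rescue, charting and return of the packet. The charting step (step 9 in both arms) reads "Document all interventions on electronic Patient Care record as per usual procedures". No step asks the paramedic to look for or record an adverse effect. Step 10 is completion of the Paramedic evaluation tool.
- **Data collection.** The Data Analysis Plan says the spreadsheet will "abstract data from the research data collection documents and the EMS electronic patient care record". It adds that "All relevant time intervals and Visual Nausea Severity Scores will be recorded for enrolled patients". The paramedic is asked to rate "ease of use, time needed to complete the treatment and their impression of effectiveness of the assigned treatment". The variables to be taken from the care record are not listed.
- **Analysis.** "Time to treatment will be compared between the two arms of the study as well as changes in Visual Nausea Severity Scores". In addition, "Treatment failures requiring additional Ondansetron will be characterized". The methods named are the t-test and confidence intervals.

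Item 7 lists expected events. For isopropyl alcohol, the likely non-serious ones are "dizziness, nausea, abdominal pain", with hypotension as less likely. For ondansetron there are eleven likely non-serious events, and three rare serious ones including dystonia and death. Item 3 says that anti-emetic agents as a group "require parenteral administration with exposure to the risks for side effects or sedation".

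**The concern.** The plan expects side effects in both arms but sets out no way to record them consistently and no comparison of them. Symptoms such as dizziness or abdominal pain are known only if someone asks. If they are not asked about during transport, the answers cannot be recovered at analysis.

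The trial proposes isopropyl alcohol as an alternative to drug treatment, in a setting where Item 2 says it has not been studied, and Item 3 supports its low inhalation toxicity from animal experiments. Tolerability in these patients is something the trial is well placed to report. As written, it could reach a conclusion on nausea with no dependable statement on harm in either arm.

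**Working it through.** **Step 1. Set the planned data against the expected events.**

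| Item 6 data element | Informs on side effects? |
|---|---|
| Time intervals | No |
| Nausea scores | No; this is the outcome |
| Rescue ondansetron | No; this marks treatment failure |
| Paramedic ratings (three named) | No side-effect item named |
| Care record, variables unlisted | Possibly, through usual charting only |

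Only the last row could carry harms data. The one relevant instruction there concerns interventions, not symptoms.

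**Step 2. Count the events in Item 7.** Isopropyl alcohol has 4 (dizziness, nausea, abdominal pain, hypotension). Ondansetron has 3 serious and 11 non-serious, so 14. Dizziness is on both lists: 4 + 14 − 1 = 17 distinct events. It is rated likely in both arms, so it is an obvious comparison that the plan does not make.

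**Step 3. Judge what usual charting can support.** A positive note shows that an event was seen. A blank may mean that the event was absent or that nobody asked. The proportion with the event is therefore not estimable without assuming that blanks mean absent. The ondansetron arm involves an injection and the isopropyl alcohol arm does not, so the intensity of charting may also differ by arm. That last step is inference; the documents do not describe the record's format.

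**Step 4. What systematic recording would give.** The documents contain no harms figure to reproduce. Inputs: 400 patients (Item 6, stated as a minimum goal). Assumptions: 1:1 allocation, so n = 200 per arm, and a common event rate p in both arms. Neither is given in the documents.

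Half-width of the 95% interval for a risk difference = 1.96 × √(2p(1 − p)/n):

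- p = 5%: 1.96 × √(2 × 0.05 × 0.95/200) = 1.96 × 0.0218 = 4.3 points
- p = 10%: 1.96 × √(2 × 0.10 × 0.90/200) = 1.96 × 0.0300 = 5.9 points
- p = 20%: 1.96 × √(2 × 0.20 × 0.80/200) = 1.96 × 0.0400 = 7.8 points

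Power at two-sided 0.05 with 200 per arm, again for assumed rates: 80% for 5% against 13% and for 10% against 20%, but 47.5% for 5% against 10%.

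Rare events: with no events among 200, the one-sided 95% upper bound is 1 − 0.05^(1/200) = 1.5%. The chance of seeing at least one event in an arm is 1 − (1 − p)^200, which is 87% at a true rate of 1% and 18% at 0.1%.

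**The case against.** Several objections have force.

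- **The care record is a data source.** This stands. A reader might infer that harms data will not exist at all, and the documents do not support that. Events such as hypotension may be found in the record. What is missing is systematic capture and any plan to use it.
- **The paramedic form and score cards are not reproduced.** This also stands. Their content is known only from the description in the Data Analysis Plan, so one can say that no side-effect item is specified, not that none is collected. Even if the form has one, no analysis of it is planned.
- **Fewer side effects is not the trial's claim.** A reader might infer from Item 3 that it is part of the case for isopropyl alcohol. The support is thin. The remark concerns anti-emetics as a group, while the same section describes side effects of prehospital ondansetron as infrequent and names cost and injection as the barriers. Items 2 and 4 rest on simplicity, cost, non-invasiveness and effectiveness, and no objective mentions fewer side effects. The point rests on Item 7 instead.
- **The trial does not propose to replace ondansetron.** Correct. The documents describe an alternative and a basic-life-support option, and ondansetron remains the rescue treatment.
- **A full tick list would work badly.** A line for all 17 events would include the outcome itself (nausea) and events hard to assess in transport, such as reduced urine output. Without reference to the state before treatment it would mix presenting complaints with treatment effects. The list therefore has to be short and restricted to change since treatment.

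**Conclusion.** The point holds in a limited form. Item 6 specifies no side-effect item and no safety analysis, while Item 7 expects events in both arms. Incidental information may be found in the care record, but a reliable comparison by arm is not possible as written. This is a gap in data collection as well as in wording, because unasked questions cannot be answered afterwards.

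Its size is modest. Assuming 200 per arm and event rates of 5% to 20%, systematic recording would give intervals of about ±4.3 to ±7.8 points. That is useful for common, mostly minor events. It would not settle rare serious ones such as dystonia or death, and it has no bearing on the nausea comparison. It should be corrected before enrolment because the remedy is cheap then and unavailable later.

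**What to change.** 1. **Form.** Add to the Paramedic evaluation tool (step 10, both arms) a short yes/no list of events that are new or worse since treatment and observable in transport, drawn from Item 7. Examples are dizziness, abdominal pain, hypotension, headache, confusion, blurred vision, abnormal movements, and other. Leave out nausea, which is the outcome. For each event, mark whether it began before or after rescue, because rescue ondansetron in the isopropyl alcohol arm blurs attribution.
2. **Care record.** Name in the Data Analysis Plan the variables to be abstracted, for example blood pressure where recorded, and apply the same abstraction rules in both arms.
3. **Analysis.** Report the number and proportion with each event, and with any event, by randomised arm, with the risk difference and 95% confidence interval. Use a score-type interval where counts are small. Show events before and after rescue separately as description, and state how many forms were incomplete. Present the table as estimation and say that it cannot exclude rare serious harms.

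The cost is a few lines on a form already completed for every patient, one table, and slightly more paramedic time. The recording paramedic knows the treatment given, so reporting is unblinded and subjective symptoms may be reported differently by arm. That limitation should be stated with the results.

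### Declared an equivalence study, but the analysis tests only for statistical significance: no margin or rule for concluding equivalence is given

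*Combined protocol and SAP*

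**What the plan says.** The abstract in Item 2 sets the design: "This will be a randomized equivalence study comparing the reduction" in reported nausea between ondansetron and inhaled isopropyl alcohol.

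The Data Analysis Plan in Item 6 describes the comparison as "Time to treatment will be compared between the two arms of the study as well as changes in Visual Nausea Severity Scores". On rescue it says "Treatment failures requiring additional Ondansetron will be characterized". Its only inferential statement is "T-test and confidence intervals will be utilized to determine statistical significance".

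The only design figure is in Item 6, Procedures and Logistics: "The goal is to enroll at least 400 patients over a 1 year period". The form asks for a sample size calculation where applicable, and none is given. No margin, alpha, confidence level, power, SD or allocation ratio appears in the readable text. After the abstract, equivalence is not mentioned again as a feature of this trial; the Background uses the idea only for other antiemetics.

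**The concern.** A significance test has two outcomes: a difference is shown, or it is not. Neither amounts to equivalence. Failing to reject zero difference is compatible with no difference, and also with a real difference that the trial was too imprecise to detect.

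A confidence interval can support equivalence, but only against a margin set in advance. Here the interval is assigned to significance and has no margin to be held against. The declared question and the stated analysis therefore do not meet.

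The practical risk is that a p-value above 0.05 gets reported as showing the two treatments equivalent. A margin chosen once the results are known would not control the error either.

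**Working it through.** **1. The texts side by side.** Item 2 asks whether the treatments are equivalent. Item 6 answers whether there is statistical significance, most naturally read as a test of zero difference. This mismatch follows from the wording alone and needs no assumed number.

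**2. The plan's own figure.** The 400-patient goal cannot be reproduced, because no margin, SD, alpha or power is given.

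**3. Inputs for illustration.**
- From the document: 400 patients and a 0–10 score.
- Assumed: 1:1 allocation (200 per arm), two-sided 0.05, and SD of the change score 2.5 / 3 / 3.5 points.
- Standard error of the difference = SD × √(2/200) = SD × 0.1, that is 0.25 / 0.30 / 0.35.
- Critical t on 398 degrees of freedom: 1.966.

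**4. How often a real difference would be non-significant.** P(|T| < 1.966), with T non-central t and non-centrality Δ/SE. Example at SD 3, Δ = 0.5: 0.5/0.30 = 1.667, and Φ(1.966 − 1.667) = Φ(0.299) ≈ 0.62.

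| True difference | SD 2.5 | SD 3 | SD 3.5 |
|---|---|---|---|
| 0.5 points | 48.6% | 61.7% | 70.3% |
| 1 point | 2.1% | 8.6% | 18.7% |
| 1.5 points | 0.003% | 0.12% | 1.03% |

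These are error rates only if non-significance is taken to mean equivalence.

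**5. What a just non-significant interval looks like.** The 95% half-width is 1.966 × SE = 0.49 / 0.59 / 0.69. An interval with one end at zero reaches twice that: 0.98 / 1.18 / 1.38 points. For any margin M below those values, a non-significant result can coexist with an interval that extends beyond M.

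**6. What an interval-within-margin rule would do.** It caps sampling error at the margin at 2.5% (95% interval) or 5% (90% interval, equal to two one-sided tests at 0.05). It does not cap bias. With no true difference, power ≈ 2Φ(M/SE − critical value) − 1. Example at SD 3, M = 1, 95% interval: 1/0.30 − 1.966 = 1.367, and 2Φ(1.367) − 1 ≈ 0.83. The values below integrate over the sample SD.

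| Quantity (true difference 0) | Interval | SD 2.5 | SD 3 | SD 3.5 |
|---|---|---|---|---|
| Power, 200 per arm, M = 1 | 95% | 95.8% | 82.8% | 62.7% |
| | 90% | 98.1% | 90.8% | 77.3% |
| Smallest M with 80% power, 200 per arm | 95% | 0.81 | 0.98 | 1.14 |
| | 90% | 0.73 | 0.88 | 1.03 |
| Patients per arm for 80% power, M = 1 | 95% | 133 | 191 | 259 |
| | 90% | 108 | 155 | 211 |

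**7. A more favourable SD.** At SD 2 the SE is 0.20. A 0.5-point difference has non-centrality 2.5 and is missed with probability Φ(1.966 − 2.5) ≈ 30%. The smallest M with 80% power falls to about 0.65 (95% interval) or 0.59 (90% interval).

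These figures show what 400 patients can support. They are not a basis for choosing M.

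**The case against.** The strongest reply is that the gap is one of omission. Confidence intervals are already planned, and an interval is what an equivalence conclusion needs. The analysis sentence is generic: it closes a paragraph that also covers time to treatment, rescue and paramedic ratings, and it names no null hypothesis. The word equivalence describes this trial only once, while Item 4 speaks of an effective alternative, so the label may be the mistake. The Item 4 text breaks off mid-sentence and the front page was not available, so a margin stated there cannot be excluded. The SDs, alpha and allocation above are assumed, and the plan never says that non-significance will be read as equivalence.

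Much of this is fair. Reading the test as one against zero is an interpretation, though the natural one. The claim reaches only as far as the readable text. The error rates are conditional and do not carry the conclusion, and nothing here shows that 400 is too few.

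The mismatch survives. The stated purpose of both the test and the intervals is significance, and the analysis section points to no margin elsewhere. If the label is the mistake, the document still has to be changed.

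**Conclusion.** The concern holds and must be fixed before analysis. The study is declared as an equivalence study, and the plan as written contains nothing by which equivalence could be concluded. That conclusion rests on the text and on no assumed figure.

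The size of the risk is conditional. Within the SD range of 2.5 to 3.5, reading non-significance as equivalence would pass a true 0.5-point difference in about half to 70% of trials and a 1-point difference in about 2 to 19%; at 1.5 points the risk is about 1% or less. Whether any of these matters depends on the unstated margin and SD. At M = 1 and 200 per arm, power for a proper equivalence rule would run from 63 to 96% with a 95% interval, or 77 to 98% with a 90% interval.

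**What to change.** Keep the planned comparisons and add to the Data Analysis Plan, in substance:

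- The primary analysis is the two-sided confidence interval for the between-arm difference in mean reduction in the Visual Nausea Severity Score. The level is stated in advance: 95%, or 90% for two one-sided tests at 0.05.
- Equivalence is concluded only if the whole interval lies within ±M, with M justified clinically and fixed before any between-arm results are seen.
- A non-significant t-test will not be interpreted as equivalence.

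Then check 400 patients against M, the chosen level and a stated SD, and report the power available. If no margin can be justified, remove the equivalence label and report a comparison with its confidence interval.

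Two separate matters must be settled for the rule to work:

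- **Which score is primary.** Item 2 and Procedures and Logistics call for scoring "upon arrival to the Emergency Department and 15 minutes after treatment whichever comes first". Step 6 of the ondansetron checklist refers to 10 minutes, and step 6 of the isopropyl alcohol checklist to "upon arrival to the Emergency Department at indicated time intervals". These passages must be reconciled so that one score can be named, with a rule for patients who reach the Emergency Department before the named time.
- **Rescue.** Step 7 of the isopropyl alcohol checklist reads "If patient still has significant nausea and or vomiting after ten minutes provide rescue Ondansetron therapy", and the ondansetron checklist has a parallel step. State the analysis set and how scores taken after rescue enter the primary analysis.

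The decision rule costs analysis-plan wording, a justified margin and a stated level. Naming the primary score may also need checklist wording. The downsides are that an inconclusive result becomes possible and that 400 may fall short of 80% power if M is small and the SD high. At M = 1 and SD 3.5 the total would be 2 × 259 = 518 (95% interval) or 2 × 211 = 422 (90% interval). In that case, state the power actually available, 63% or 77% at 200 per arm. Dropping the label costs only wording but gives up the declared question.
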